1. Study Summary

Project Title	Biomarker-Based Approaches to Understand and Predict Cardiovascular Toxicity from Androgen Deprivation Therapy Targeting the Gonadotropin Releasing Hormone Pathway in Prostate Cancer Men
Project Design	Open-label randomized clinical trial with parallel prospective cohort study
Primary Objective	Elucidating the pathophysiologic link between gonadotropin releasing hormone agonist hormone therapy (e.g. Lupron) and cardiovascular (CV) toxicity, and the mechanism by which CV risk-reduction is achieved by the novel oral GNRH-antagonist, relugolix. This objective will be studied using imaging and blood biomarkers.
Secondary Objective(s)	Identify genomic alterations that predispose an individual to enhanced CV toxicity following hormone therapy with GNRHa or relugolix
Research Intervention(s)/Interactions	A) GNRHa versus relugolix [randomization] B) Parallel, non-interventional cohort of men receiving no hormone therapy
Study Population	Men >18 years with localized intact or recurrence prostate cancer undergoing radiation therapy (with or without prior prostatectomy), with or without hormone therapy
Sample Size	90 men (30 men in GNRHa arm, 30 men in relugolix arm, 30 men in non-hormone therapy cohort)
Study Duration for individual participants	12 months
Study Specific Abbreviations/Definitions	Radiation therapy (RT) Androgen deprivation therapy (ADT) Gonadotropin-releasing hormone agonist (GNRHa) Gonadotropin-releasing hormone antagonist (GNRHaa) Nonsteroidal anti-androgen (AA) Combined androgen blockade (CAB) Major adverse cardiac events (MACE)
Funding Source (if any)	Prostate Cancer Foundation-Pfizer-Myovant Challenge Award, Prostate Cancer Foundation Young Investigator Award

2. Objectives

Androgen deprivation therapy (ADT) with a gonadotropin-releasing hormone agonist (GNRHa) is a highly effective and commonly used treatment for prostate cancer (PCa) with over 500,000 men with PCa receiving ADT annually in the United States^{3,4}. However, large observational studies suggest GNRHa is associated with increased risk of myocardial infarction (MI) and sudden cardiac death, raising concerns that ADT causes cardiovascular (CV) harm⁴⁻⁶. In fact, as more men survive PCa due to increasing ADT use, **CV**

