The role of ADT in CV harm was ignited with the publication of large observational studies in the past decade, which suggested that ADT use in the form of a GNRHa for PCa men was associated with a 20% increased risk of CAD, 10-30% increased risk of MI, and a 15% increased risk of sudden cardiac death⁴⁻⁶. With increasing ADT use and improving radiation/surgical technique, ***CV mortality, not cancer, is now the most common cause of death in PCa patients***^{7,8}. Additionally, while the addition of ADT with radiation therapy has been shown to improve survival for men with unfavorable risk PCa, multiple post-hoc studies have suggested that the addition of ADT may result in a survival *detriment* in men with CV comorbidities^{13,14}.

Traditionally, CV injury following ADT is thought to be driven by an indirect mechanism of prolonged hypogonadism precipitating metabolic syndrome, insulin resistance, and weight gain over several years^{7,15-17}. However, the effect of ADT, namely GNRHa, may be direct. There are several observations from recent studies that support this premise. First, studies have shown that ADT, after only 3-6 months of therapy, is associated with an increased risk of atherothrombotic events^{7,8}. Second, data from the recent HERO trial² evaluating GNRHa (leuprolide) versus GNRH-antagonist (relugolix) in PCa men showed an increased incidence of major adverse CV events with GNRHa compared with GNRH-antagonist as soon as 4 weeks after initiation of treatment (Figure 1). Further, testosterone suppression was greater with GNRH-antagonist than GNRHa, countering the testosterone-mediated CV effect. Finally, the excess CV event risk with ADT in the large observational studies mentioned above⁴⁻⁶ was seen with GNRHa therapy, not orchiectomy/surgical castration. In fact, meta-analysis of several observational studies⁵ have shown a hazard ratio for risk of MI with GNRHa (compared with other forms of ADT) to be 1.57 (95% CI 1.26-1.94). Nonetheless, GNRHa remains the most widely utilized form of ADT in the United States due to lower cost, convenience in delivery, and minimal injection-associated adverse effects compared with injectable GNRH-antagonist.

[figure not shown]

Figure 1. Incidence of major adverse cardiac events (MACE) in men with advanced PCa receiving leuprolide versus relugolix. Incidence curves separate immediately after onset of treatment, with GNRHa resulting in more MACE².

Association of Immune Response and Coronary Atherosclerosis

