Numerous genetic alterations have been shown to result in either enhanced or diminished ability to mount inflammatory immune responses, including genes associated with 'clonal hematopoiesis of indeterminate potential' (CHIP) such as DNMT3A, TET2, ASXL1, PPM1D, KDM6A, and BCOR⁵³⁻⁵⁵, as well as several others that alter inflammatory immune function⁵⁶⁻⁶². The impact of these immune-related genomic alterations on the development of inflammatory immunity and CV toxicity following ADT will be examined in Aim 3, testing the underlying hypothesis that **somatic mutations associated with enhanced effector responses lead to increased CV injury in men receiving GNRH agonists but not relugolix.**

5. Study Intervention/Investigational Agent

Hormone Therapy Intervention

For men who will be receiving ADT with radiation therapy, there will be a 1:1 randomization between GNRHa (i.e. leuprolide or triptorelin) versus oral relugolix. Dosing for these agents are per standard FDA-approved guidelines, and the study has no impact on dose or duration of therapy.

For men receiving GNRHa, standard FDA-approved intramuscular or subcutaneous injectable doses will apply (i.e. leuprolide 7.5 mg monthly, 22.5 mg q3month, 45 mg q6month; triptorelin 11.25 mg q3month, 22.5 mg q6month). Each patient may receive 21-30 days of oral bicalutamide 50 mg daily beginning at the time of first injection (i.e. to hinder the initial testosterone flare associated with GNRHa) at the discretion of the treating provider. Duration of therapy will depend on the risk category of prostate cancer, as detailed in section 6.

For men receiving oral relugolix, standard FDA-approved oral doses will apply (i.e. 360 mg on day 1, followed by 120 mg daily for the duration of therapy). The tablet is in doses of 120 mg, and it can be taken by mouth with or without food. If the subject misses > 7 days of medication, then a loading dose of 360 mg will be initiated followed by re-initiation of 120 mg daily thereafter. Participants will be asked to complete a drug diary and bring the diary in addition to medication for reconciliation at each follow up visit. Duration of therapy will depend on the risk category of prostate cancer, as detailed in section 6.

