Men with localized intact PCa, or non-metastatic recurrence following prostatectomy, and prescribed radiation therapy (XRT) with or without concomitant ADT will be consented and enrolled on this prospective trial. Eligible subjects are men > 18 years old diagnosed with non-metastatic PCa planning to undergo curative-intent therapy. Men with prior cardiac stent or bypass surgery will be excluded. Men with prior exposure to ADT will be excluded.

Each patient will undergo external beam XRT with or without concomitant ADT of 6-24 months duration. **For those men with National Comprehensive Cancer Network (NCCN)-defined unfavorable intermediate- or high-risk disease, or with biochemically recurrent PCa requiring salvage XRT plus ADT, each will be randomized 1:1 between injectable intramuscular or subcutaneous GNRHa depot (leuprolide 22.5 mg every 3 months, leuprolide 45 mg every six months) versus GNRH-antagonist (oral relugolix 360 mg loading dose followed by 120 mg daily).** Men with NCCN-defined low- or favorable intermediate-risk intact disease, or those with biochemically recurrent PCa requiring salvage XRT without ADT, will be treated with XRT alone. Each patient will provide consent for (1) pre-treatment and 12-month post-ADT prospective ECG-gated, contrast-enhanced CCTA and (2) peripheral blood banking at baseline and at 3-, 6-, and 12-months post-treatment (**Figure 5**).

Figure 5. Study Schema

ADT randomization will be created using preconstructed allocation sequences using maximal randomization (<https://ctrandomization.cancer.gov/tool/>). Patients will undergo a pre-randomization stratification based on Atherosclerotic Cardiovascular Disease (ASCVD) risk score (low/intermediate versus high). All principal investigators and co-investigators will be blinded to this randomization block. Lead statistician ([name]) and clinical research coordinators will have access to this allocation sequence.

Methods: As seen in above study schema, each patient in each cohort will undergo pre-treatment and 12-month post-ADT initiation coronary CT. Each patient will undergo a non-contrast CT scan using standard

Protocol Title: Mechanism and Predictors of Cardiotoxicity after Prostate Cancer Treatment: A Parallel Cohort and Randomized Trial Comparing Radiation Alone, Radiation plus Leuprolide, and Radiation plus Relugolix

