coronary artery calcium (CAC) imaging protocol for coronary calcium quantification prior to the acquisition of the CCTA. CAC images will be obtained using prospective ECG-triggering at 70% of the R-R interval, using tube voltage of 120 kV and an automated tube current modulation and minimum slice collimation (0.6 mm). Images will be reconstructed in 3 mm slice thickness at 3 mm intervals. Following CAC scan, contrast-enhanced CCTA will be performed using an ECG-gated, single-beat acquisition scan to include 30-80% of the R-R interval. Scanning will extend from the tracheal bifurcation to 2 cm below the left ventricular apex; 0.5 mm detector collimation will be used.

Additionally, peripheral blood will be drawn and stored in our established biorepository (under protocol WINSHIP5179-20) at the following intervals: pre-treatment, and 3-, 6-, and 12-months post-ADT initiation. Further details regarding analysis plan of peripheral blood below in Aims 2 and 3.

Aim 1.1: To determine the relationship between ADT (i.e. GNRHa versus relugolix) and accelerated coronary plaque development and/or rupture in PCa men, all contrast enhanced CCTA images will be analyzed using a commercially-available, validated artificial intelligence-guided imaging analysis service (HeartFlow, Inc, Mountain View CA). Multiplanar reconstructed images will be assessed for the presence, volume, and qualitative composition (e.g. total, calcified, non-calcified, mixed) of atherosclerotic plaque for each coronary artery segment. Luminal stenosis will be graded on an ordinal scale 0-100%. CCTA scans pre- and 12 months post-treatment will be compared. We hypothesize that ***men receiving GNRHa will be at increased risk of total plaque volume increase compared with men receiving relugolix or no ADT.***

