Study participant research data, which is for purposes of statistical analysis and scientific reporting, will be transmitted to and stored. This will not include the participant's contact or identifying information. Rather, individual participants and their research data will be identified by a unique study identification number. The study data entry and study management systems used by clinical sites and research staff will be secured and password-protected. At the end of the study, all study databases will be de-identified and archived.

21. Economic Burden to Participants

The costs of the patient's primary treatment, including pre-treatment consultation and necessary evaluations, simulation, XRT treatment course, and follow-up surveillance laboratory studies are expected to be covered by the patient's insurer/primary payor. For patients randomized to receive relugolix for ADT with XRT, drug will be provided by Myovant Sciences as part of the funding source (Pfizer-PCF-Myovant Challenge Award).

All blood draw appointments for the biorepository correspond to intervals of standard blood draws for cancer surveillance.

Patients will incur costs associated with travel and time (with non-routine coronary CT that will be taken pre-treatment and 12-months after initiating ADT (two imaging scans total per patient). Patients will be compensated \$200 total (distributed at 2 intervals of \$100 each, detailed above) to account for gas mileage usage for appointments/tests required on trial.

22. Informed Consent

This study will enroll patients with localized prostate cancer, or biochemically recurrent prostate cancer after prior prostatectomy, who are candidates for curative-intent radiation therapy (with or without ADT). Men who do not receive ADT will be enrolled on a prospective, single-arm cohort; men who are eligible for ADT will be randomized between two FDA-approved, guideline-supported ADT agents: (1) GNRHa (e.g. Lupron, Trelstar) or (2) Relugolix.

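### Sections 1, 5, 6 and 22 use different rules for who enters the radiation-alone cohort, so a man with an ADT indication who is not given ADT has no settled place and the non-randomized no-ADT contrasts could be confounded

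*Combined protocol and SAP*

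**What the plan says.** Four places in the combined protocol and SAP decide who is randomized and who joins the cohort.

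- **Section 1 (Study Summary)** describes the cohort by receipt: "Parallel, non-interventional cohort of men receiving no hormone therapy".
- **Section 5 (Study Intervention)** randomizes by planned receipt: "For men who will be receiving ADT with radiation therapy, there will be a 1:1 randomization".
- **Section 6 (Procedures Involved)** goes by cancer risk for intact disease. Unfavorable intermediate- and high-risk men are all randomized. For recurrence it goes by whether the salvage plan includes ADT. Radiation alone is for "Men with NCCN-defined low- or favorable intermediate-risk intact disease, or those with biochemically recurrent PCa requiring salvage XRT without ADT".
- **Section 22 (Informed Consent)** uses two criteria in one sentence: "Men who do not receive ADT will be enrolled on a prospective, single-arm cohort; men who are eligible for ADT will be randomized".

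The Section 10 eligibility list contains no NCCN criterion and nothing specific to the cohort. In Section 6, stratification by ASCVD score is described only as a step before randomization. The Aim 1.1 analysis plan gives age and statin use as examples of confounders. It does not name ASCVD risk, baseline plaque or the reason for no ADT.

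**The concern.** Receipt and eligibility are not complements. A man can have a cancer indication for ADT and still not be given it, because he declines or because it is omitted. No section says where he goes.

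This matters because the cohort is a named comparator on the primary endpoint: the Aim 1.1 hypothesis is that GNRHa carries a higher risk of "total plaque volume increase compared with men receiving relugolix or no ADT". Section 3 also reports that "multiple post-hoc studies have suggested that the addition of ADT may result in a survival" detriment in men with cardiovascular comorbidity. A clinician aware of that might hold ADT back from a man with heart risk. If such men entered the cohort, the comparator would be selected partly on a risk factor for the outcome. Faster plaque growth among them would shrink an apparent GNRHa effect against no ADT and would flatter relugolix against no ADT.

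**Working it through.** **Step 1. Apply each rule to two test cases.** Man A has intact, high-risk disease and will not be given ADT. Man B has a recurrence, and his salvage plan omits ADT.

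| Place | Criterion | Man A | Man B |
|---|---|---|---|
| Section 1 | receipt | cohort | cohort |
| Section 5 | planned receipt | not randomized; cohort not mentioned | not randomized; cohort not mentioned |
| Section 6 | NCCN group, or salvage plan | randomized | cohort |
| Section 22, first clause | receipt | cohort | cohort |
| Section 22, second clause | eligibility, undefined | randomized, if eligible means a cancer indication | depends on what eligible means |
| Section 10 | none | admitted, not assigned | admitted, not assigned |

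Man A gets opposite answers. If eligible means a cancer indication, he is to be randomized between two drugs of which he will take neither. If it means fit and willing to take ADT, he falls into the cohort. For Man B the places largely agree, but the criterion is the treatment decision itself, so selection on clinical judgment is possible within Section 6 alone.

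**Step 2. Reproduce the plan's figure.** The Section 6 power paragraph gives 30 per group, SD 30 mm³, difference 20 mm³ and 80% power. It states neither alpha nor sidedness. The standard error is 30 × √(2/30) = 7.75, and 20/7.75 = 2.58. The normal approximation gives:

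- one-sided 5%: Φ(2.58 − 1.645) = 82.6% (81.8% by noncentral t)
- two-sided 5%: Φ(2.58 − 1.96) = 73.3% (71.9% by noncentral t)

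The stated 80% is close to the one-sided figure. That is a separate matter, so both are carried forward.

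**Step 3. Illustrate the possible size.** Let f be the share of the 30 cohort men who have an indication but were left off ADT. Let d be their excess mean 12-month plaque change over the other cohort men. Neither is in the documents; f = 10-30% (3 to 9 men) and d = 10-30 mm³ are assumptions.

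- Bias = f × d, and the apparent difference = 20 − f × d.
- Cohort SD = √(30² + f(1 − f)d²), and SE = √(30²/30 + cohort SD²/30).
- Power = Φ((20 − f × d)/SE − z).

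| f | d (mm³) | Bias (mm³) | Apparent difference (mm³) | Power, two-sided 5% | Power, one-sided 5% |
|---|---|---|---|---|---|
| 10% | 10 | 1 | 19 | 68.7% | 78.9% |
| 10% | 30 | 3 | 17 | 57.4% | 69.2% |
| 20% | 10 | 2 | 18 | 63.8% | 74.8% |
| 20% | 30 | 6 | 14 | 41.3% | 53.8% |
| 30% | 10 | 3 | 17 | 58.8% | 70.4% |
| 30% | 30 | 9 | 11 | 27.1% | 38.4% |

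The sign is also open. With d = 0 there is no bias. With d = −10, the apparent difference rises to 21-23 mm³ over the same shares.

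**Step 4. Scope.** The cohort does not enter the GNRHa versus relugolix comparison, so the bias there is zero. The rule may change which men reach randomization, but both arms are drawn from the same men.

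**The case against.** Section 22 has to be read whole. After the cohort clause it says "men who are eligible for ADT will be randomized between two FDA-approved, guideline-supported ADT agents", and Man A arguably falls under that clause. Section 22 is also a summary written for consent, whereas Section 6 is the operative text and is explicit for intact disease. This stands to the extent that Section 22 is ambiguous; it does not plainly admit men with an indication. A reader might infer that it sends every man without ADT, including those spared it for heart risk, into the comparator. The sentence does not support that.

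The heart-risk mechanism is inferred. Section 3 is background, and no section describes withholding ADT for cardiac reasons. Stratifying by ASCVD score implies that high-risk men are expected among those randomized. Section 10 excludes men with earlier coronary revascularization or an implanted cardiac device. Section 8 keeps scan findings blinded until the second scan, so the baseline scan should not steer the decision. All of this stands, and it limits how far the mechanism can be pressed. Other cardiovascular comorbidity is still admitted.

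Adjustment is possible. Every man has a baseline CCTA and calcium scan, the outcome is change from baseline, and the confounder list is open-ended. The fair criticism is only that the relevant covariates are not prespecified.

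Finally, the cohort is openly non-randomized and already differs by cancer risk. Consistent wording will not remove that difference.

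**Conclusion.** The inconsistency is real and sits in the text: the four places do not give one answer for a man with an ADT indication who is not given ADT, and Section 10 does not supply it. For salvage men, Section 6 itself follows the treatment decision.

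Confounding of the GNRHa or relugolix versus no-ADT contrasts is possible if heart risk influences who goes without ADT. A reader might go further and conclude that the cohort will hide a GNRHa effect or make relugolix look as good as no hormone therapy. The documents do not support that: they give neither the share of such men nor their plaque growth, and the net direction of imbalance between cohort and ADT arms cannot be established. The 1-9 mm³ range (5-45% of the 20 mm³ design difference) and the power figures rest wholly on assumed inputs. The upper end needs 9 of 30 cohort men with an excess equal to one full planning SD, or 1.5 times the design difference.

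The primary randomized contrast is unaffected. This is an inexpensive improvement to a secondary comparator, not a flaw that threatens the trial.

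**What to change.** 1. Reconcile Sections 1, 5, 6 and 22 under one cohort-membership rule, define eligibility for ADT, and record each man's classification before consent.
2. Flag any man with an ADT indication who does not receive it, and leave him out of the main contrasts with no ADT.
3. Record the reason for no ADT for every cohort man, including salvage men, at enrollment.
4. Repeat the no-ADT contrasts without men for whom cardiovascular risk was the reason.
5. Prespecify baseline ASCVD risk and baseline total plaque volume as covariates in the cohort contrasts. The ASCVD score must then be obtained in cohort men too, since the plan describes it only for stratifying before randomization.

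The cost is wording in four sections, one screening-log field, the ASCVD score for cohort men and a short addition to the Aim 1.1 analysis plan. Accrual of the 30 cohort men may be slightly slower. The change concerns cohort membership and analysis only; it alters no one's treatment.
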